**Effect of Probiotics on Amino Acid Absorption- Study Protocol**

IRB Approval No.: 2022180

Date: 16/02/2023

**Aim:** This project aims to investigate the effect of probiotics on amino acid absorption after the consumption of a plant-protein beverage.

### Study Design:

This study is a randomized crossover study to assess the amino acid concentration in the blood after the consumption of a plant protein beverage. The plant protein beverage is formulated and developed in SIT. The study will take place over a duration of 10 to 12 weeks, following the schedule depicted below in Figure 1. The study has already been approved by SIT-IRB.

[figure not shown]

Figure 1: Schematic diagram of Study Visits

For this study, 20 healthy participants will be recruited. Inclusion criteria include healthy body weight (BMI 18.5-23kg/m^2), and lack of any underlying medical conditions. Exclusion criteria include any individuals who were treated for or diagnosed with a gastrointestinal, cardiac, respiratory, circulatory, musculoskeletal, metabolic, immune, autoimmune, haematological, neurological or endocrinological disorder, and having any form of food allergy/intolerances/avoidances, in particular allergies to eggs, soya, peanuts, tree nuts, crustaceans, and gluten. Participants are not allowed to consume any nutritional supplements known to affect measures of the current study for 8 weeks of supplementation and washout periods, including probiotics, prebiotics, synbiotics and/or digestive enzymes. Participants who are unable to be weight stable defined as measured body mass deviating by 2% or more, and participants who were not willing to abstain from alcohol, nicotine, and caffeine for 12h prior to each study visit are also excluded.

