### Screening, Consent and Recruitment

Participants will be recruited using recruitment advertisements sent via mass email to SIT staff and students using email distribution lists. A briefing for all potential study subjects on the nature and purpose of the study, roles and responsibilities of the study subjects, study procedures, risk and benefits and other relevant information will be carried out. All potential subjects will be given a participant information sheet and informed consent form if they wish to participate in the study after the briefing. The PI will also be available for any clarification either through in-person or email.

Recruited participants will be provided a stool collection kit. Once stool sample is collected, participant will contact the study team for collection. The stool sample will be sent to AMILI's lab for analysis, for the prescription of personalized probiotics from among different probiotic cocktail formulations commercially

offered by AMILI.

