### **PRE-visit**

After informed consent, the study team will arrange for the participants to collect their personalized probiotics / placebo supplements and commence their supplementation period of 2 weeks before each study visit. Participants will be randomly assigned the probiotics or placebo supplementation arm using an online randomization software (<https://www.randomizer.org/>). Unblinding will only take place upon completion of all participants' study visit.

The PLA (placebo) capsules will consist of maltodextrin. The PRO (probiotics) supplements are commercially available products offered by AMILI. All study participants will complete the Lifestyle Questionnaire designed by AMILI and undergo a stool sample analysis to determine the which formulation of probiotics supplement they will receive. All participants will consume the PLA/PRO supplement capsules daily for 2 weeks.

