### **Study Visits 1 and 2**

At the end of each supplementation period, participants will report to SIT@Dover between 0800-1200 after an overnight 10-12h fast for their study visit (Visits 3 and 4 in Figure 1). There will be a washout period of 4 weeks between supplementations.

Both study visits will involve:

1. Anthropometric measurements.

Weight and height will be measured and used to calculate Body Mass index. Body composition will be measured using bioimpedance analysis. Blood pressure and resting heart rate will also be taken. All measurements will be taken before blood draw.

2. Diet History

A diet history will be performed at each study visit to obtain information about the usual dietary practices of participant. SIT Dietetics and Nutrition students will be engaged to assist in collecting this participant diet history information by the PI, [name].

3. Serial blood draw

Peripheral intravenous cannula will be inserted into antecubital vein for multiple blood sampling (5ml per collection). A baseline blood sample will be drawn at 0 min, after which participants will consume the beverage within 15 mins. Serial blood samples will be taken at 15, 30, 45, 60, 90, 120, 150 minutes after participant began consuming the plant protein beverage.

After each 5 ml blood sample is drawn, the cannula will be flushed with 2 ml normal saline to ensure patency until the next blood draw time. Upon the completion of the blood draw and removal of cannula, the venipuncture site and overall condition of the participant will be examined before the participant leaves the SIT study site, to ensure that the participant is no longer bleeding and can stand up without dizziness.

4. Stool samples will be collected using a gut microbiome test kit provided by AMILI. Participants will submit their second and third stool samples on Study Visit 1 and 2 respectively.

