### **Stool Samples Analysis**

A total of 3 stool samples will be collected from each participant to determine any changes in gut microbiome profile with probiotic/placebo supplementation. Stool samples will be stored in AMILI's laboratory prior to analysis and disposed post-analysis. Stool will be analyzed for microbiome diversity as well as functional pathways using shotgun metagenomic sequencing with the Illumina's DNA Library Preparation kit according to the manufacturer's recommended protocol. Differences in bacterial communities between pre-post samples from the same participants, and between groups with and without probiotic supplement after consumption of the plant-based protein will be compared. Taxonomic and functional profiles will also be generated.

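### The supplement ban begins with the first study capsule, so the baseline stool sample, which guides the formulation and anchors the pre-post microbiome comparison, can come from a current probiotic user

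*Combined protocol and SAP*

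**What the plan says.** All references are to the combined protocol and SAP.

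- **Ban.** Study Design prohibits supplements that could affect the study's measurements "for 8 weeks of supplementation and washout periods, including probiotics, prebiotics, synbiotics and/or digestive enzymes".
- **Timeline.** PRE-visit has participants "commence their supplementation period of 2 weeks before each study visit". Study Visits 1 and 2 adds: "There will be a washout period of 4 weeks between supplementations". Study Design gives the overall length: "The study will take place over a duration of 10 to 12 weeks".
- **First stool sample.** Screening, Consent and Recruitment states: "Recruited participants will be provided a stool collection kit". The sample goes for analysis before a product is prescribed. PRE-visit repeats that everyone will "undergo a stool sample analysis to determine the which formulation of probiotics supplement they will receive", alongside a Lifestyle Questionnaire.
- **Later stool samples.** Study Visits 1 and 2 states: "Participants will submit their second and third stool samples on Study Visit 1 and 2 respectively".
- **Use of the samples.** Stool Samples Analysis plans to compare "Differences in bacterial communities between pre-post samples from the same participants", and also to compare the supplemented and unsupplemented conditions.

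The eligibility criteria contain no exclusion for recent use of these products, and the readable text describes no run-in.

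**The concern.** The plan regards a participant's own probiotics as able to affect its measurements, and it separates its two supplementation periods by 4 weeks. It asks for no comparable interval before its first measurement. Under the rule as written, a current user can enrol, give the first stool sample while still taking another product, and stop only when the study capsules begin.

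Two uses of that sample are exposed. The prescription would be based partly on a microbiome shaped by the other product. The pre-post comparison would also start from the wrong place. In a placebo-first user, the change from sample 1 to sample 2 would include withdrawal of the participant's own product. In a probiotic-first user, it would show a switch of products rather than an introduction. This baseline cannot be collected again once supplementation has begun.

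Amino acid AUC is exposed less directly, through any effect of prior use that is still present at Study Visit 1.

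**Working it through.** **1. Length of the ban.** Period 1 (2 weeks) + washout (4 weeks) + period 2 (2 weeks) = 8 weeks. This reproduces the stated 8 weeks exactly, so no part of the ban is left for the time before period 1. The rest of the study is 10 - 8 = 2 to 12 - 8 = 4 weeks. The text does not say where those weeks fall, but sample 1 must precede the first capsule because the product is chosen from it.

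**2. Abstinence the rule guarantees.** Take a participant who stops their own product on the day the ban begins.

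| Point in the study | Weeks guaranteed |
|---|---|
| Stool sample 1 | 0 |
| Start of period 1 | 0 |
| Study Visit 1 (stool sample 2, first AUC) | 2 |
| Start of period 2 | 2 + 4 = 6 |
| Study Visit 2 (stool sample 3, second AUC) | 6 + 2 = 8 |

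**3. Stool sample 1.** The share affected is the share p of recent users among recruits. The documents do not give p. Assuming 10-40%, that is 0.10 × 20 = 2 to 0.40 × 20 = 8 participants.

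**4. Mean AUC effect.** Let E be the true probiotic-minus-placebo difference and r the fraction of a probiotic effect left at Study Visit 1. Assume nothing is left at Study Visit 2 and that half of the users take each order. Let a be the part of that residual that adds to the study product: a = 1 if fully additive, a = 0 if it adds nothing.

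- Placebo-first users: E - rE = E(1 - r).
- Probiotic-first users: E + arE = E(1 + ar).
- Mean over all participants: E[1 - 0.5 × p × r × (1 - a)].

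With a = 1 the mean is E, so dilution is zero. With a = 0 dilution is p × 0.5 × r:

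- p = 20%, r = 0.5: 0.20 × 0.5 × 0.5 = 5%. The 16-26% increase cited in the Data Analysis Plan would become 16 × 0.95 = 15.2% to 26 × 0.95 = 24.7%.
- p = 10%, r = 0.25: 1.25%.
- p = 40%, r = 1: 20%. This needs an unrelated product to match the study product fully and not to fade at all over 2 weeks.

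**5. Variance and chance imbalance.** With a = 1 and r = 0.5, users' differences are 0.5E (placebo first) and 1.5E (probiotic first). The mean is unchanged, but the between-participant variance rises by p × r² × E² = 0.20 × 0.25 × E² = 0.05E². No stratification by prior use is described. If 4 of 20 are users and order is an independent coin toss, all four are placebo-first with probability (1/2)⁴ = 1/16, and the mean then shrinks by 4 × 0.5 / 20 = 10%. The mirror-image allocation is equally likely and would inflate the mean by 10% if the residual is additive. The planned paired t-test has no stated period or sequence term.

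**The case against.** The strongest reply is that the plan is internally consistent. The ban is tied expressly to supplementation and washout, 8 weeks matches those periods, and it already runs to the last visit. A reader might infer that 8 weeks contradicts the 10-12 week study. It does not, because the two figures describe different spans. That part of the reply stands, but it leaves the start of the ban unchanged.

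Second, a reader might infer that prior users on placebo first reach their blood draws with no washout, or that they may keep taking their own product during period 1. Neither follows. The ban is in force throughout period 1, so at least 2 weeks separate own use from the first AUC.

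Third, a formulation chosen from a user's sample does not by itself bias the AUC contrast, since each participant is compared with their own placebo AUC. Basing the choice on a person's habitual microbiome may even be what the commercial service intends. This stands, and it leaves the microbiome baseline as the main exposure. The Data Analysis Plan names no test for that comparison, so no formal inference is specified there.

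Fourth, Figure 1 is not shown, the study visits are numbered 3 and 4 in it, and the questionnaire's content is not given. A run-in or a screening question could sit in either place. That limits certainty, but no readable eligibility rule supplies one.

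**Conclusion.** The gap is real and concerns mainly stool sample 1. Followed as written, the rule lets a current user of probiotics or related products supply both the prescribing sample and the only pre-supplementation microbiome baseline. It affects only prior users, and for each of them the sample may be distorted rather than certainly is. Their share is unknown; 10-40% is an assumption.

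For amino acid AUC the consequence is secondary: 2 weeks' guaranteed abstinence against 8 can add a period difference and some variance. A reader might infer that the AUC comparison is biased toward no effect. The documents do not support that as a general claim. With balanced sequences, mean dilution runs from 0 to p × 0.5 × r, and the upper end requires the residual to add nothing on top of the study product. At p = 20% and r = 0.5, both assumed, that upper end is 5%. Nor is first-period placebo unlike second-period placebo for the whole trial; any such difference is confined to prior users.

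**What to change.** Move the start of the existing restriction to before stool sample 1. The investigators should choose the interval and justify it against the 4 weeks they already require between supplementations. The end of the restriction needs no change. Record prior use of the restricted products at enrolment; if the Lifestyle Questionnaire already asks, say so and attach a rule for deferral or exclusion. If Figure 1 already contains a run-in, state it in the eligibility text.

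The cost is one eligibility sentence and perhaps one questionnaire item. A few volunteers would start later or be ineligible. If the interval equalled the washout, a current user would wait up to 4 weeks, which is noticeable against a 10-12 week schedule.

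An AUC analysis with and without recent users is optional. At 25% dropout there are 20 × 0.75 = 15 completers, and p = 20% would remove only 0.20 × 15 = 3, so it would say little. Antibiotic use before the baseline sample is a separate point and should not be folded into this change.

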### Screening, Consent and Recruitment

Participants will be recruited using recruitment advertisements sent via mass email to SIT staff and students using email distribution lists. A briefing for all potential study subjects on the nature and purpose of the study, roles and responsibilities of the study subjects, study procedures, risk and benefits and other relevant information will be carried out. All potential subjects will be given a participant information sheet and informed consent form if they wish to participate in the study after the briefing. The PI will also be available for any clarification either through in-person or email.

Recruited participants will be provided a stool collection kit. Once stool sample is collected, participant will contact the study team for collection. The stool sample will be sent to AMILI's lab for analysis, for the prescription of personalized probiotics from among different probiotic cocktail formulations commercially

offered by AMILI.

### **PRE-visit**

After informed consent, the study team will arrange for the participants to collect their personalized probiotics / placebo supplements and commence their supplementation period of 2 weeks before each study visit. Participants will be randomly assigned the probiotics or placebo supplementation arm using an online randomization software (<https://www.randomizer.org/>). Unblinding will only take place upon completion of all participants' study visit.

The PLA (placebo) capsules will consist of maltodextrin. The PRO (probiotics) supplements are commercially available products offered by AMILI. All study participants will complete the Lifestyle Questionnaire designed by AMILI and undergo a stool sample analysis to determine the which formulation of probiotics supplement they will receive. All participants will consume the PLA/PRO supplement capsules daily for 2 weeks.

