### **Serial Blood Samples Analysis**

Blood samples will be centrifuged at 1500xg for 15 min at 4°C. The resulting serum/plasma will be aliquoted, and the resultant plasma stored at -80°C before analysis. Blood samples will be analyzed for amino acid profile as well as for glucose and insulin profile. After analysis, the samples will be disposed.

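### Unblinding is permitted once all visits are complete, before at least the last visit's plasma and stool can be assayed; tie it to assay completion and data lock instead

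*Combined protocol and SAP*

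**What the plan says.** The only sentence on blinding that applies to this trial is in PRE-visit: "Unblinding will only take place upon completion of all" participants have completed their visits. Study Design calls the trial a randomized crossover and gives no level of blinding. The term double-blind appears only in the Data Analysis Plan and the References, where it describes the cited study.

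The samples come in and are handled as follows.

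- **Blood.** Study Visits 1 and 2 schedules a baseline draw and seven later draws at each visit. Serial Blood Samples Analysis has "the resultant plasma stored at -80°C before analysis", and then: "Blood samples will be analyzed for amino acid profile as well as for glucose and insulin profile". Afterwards, "After analysis, the samples will be disposed".
- **Stool.** "Participants will submit their second and third stool samples on Study Visit 1 and 2 respectively". Under Stool Samples Analysis, samples are kept at the probiotic supplier's laboratory "prior to analysis and disposed post-analysis". The planned comparisons include bacterial communities "between groups with and without probiotic supplement after consumption of the plant-based protein will be compared".
- **Supplier.** PRE-visit states: "The PRO (probiotics) supplements are commercially available products offered by AMILI". The same company's laboratory therefore handles the stool.

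The Data Analysis Plan specifies AUC by the linear trapezoidal rule on whatever time points are available, paired t-tests and a 0.05 threshold. The visible text mentions no coded samples, no masked laboratory or analyst, and no data lock.

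**The concern.** A blind protects a result until the last decision that could alter the data has been made. Here the stated trigger is the end of the visits, which comes before the end of the assays. From then on the allocation may be known while some samples are still in the freezer or at the sequencing laboratory.

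Four kinds of decision could then be taken with the condition known:

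1. whether to repeat an assay;
2. whether to exclude a value;
3. what to do with an AUC that lacks its first or last time point;
4. how to process and compare the metagenomic data, for which Stool Samples Analysis names no statistical method.

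Because samples are disposed of after analysis, a blinded repeat assay could not be added later. Decisions taken on recorded data could still be revisited blind.

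**Working it through.** The plan gives no figure for this point. The check is the order of events, followed by a count of the samples concerned.

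**Order of events**

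1. The last participant attends the last visit. Blood is drawn and the third stool sample is handed in (Study Visits 1 and 2).
2. That visit ends, so the PRE-visit condition for unblinding is met.
3. Plasma is frozen and later assayed (Serial Blood Samples Analysis). Stool is stored and later sequenced (Stool Samples Analysis).
4. AUCs are calculated and tested (Data Analysis Plan).

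Step 3 cannot precede step 1 for the last visit's samples. They are therefore assayed after unblinding is permitted, whatever the batching. For earlier visits the order is unknown, because no assay timing is stated.

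**Inputs**

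- Draws per visit: 0, 15, 30, 45, 60, 90, 120 and 150 min = 8 (Study Visits 1 and 2).
- Blood-sampling visits per participant: 2.
- Post-supplementation stools per participant: 2. The first stool precedes supplementation and is not counted.
- Participants: 20, with assumed drop-out of 20-30% (Data Analysis Plan).

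**Count**

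| Scenario | Plasma samples | Post-supplementation stools |
|---|---|---|
| Certain minimum: last visit only | 1 × 8 = 8 | 1 |
| No assay started, 16 or 14 completers only | 16 × 2 × 8 = 256, or 14 × 2 × 8 = 224 | 16 × 2 = 32, or 14 × 2 = 28 |
| No assay started, no drop-out | 20 × 2 × 8 = 320 | 20 × 2 = 40 |

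The completer counts are 20 × (1 − 0.20) = 16 and 20 × (1 − 0.30) = 14. The last two rows assume that every assay waits until the visits are over, which the protocol does not say.

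**What is already settled**

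The instruction to use the available time points largely settles a missed interior draw: the trapezoid joins the neighbouring values. It does not settle a missing endpoint. Without the 0-min value the curve spans 150 − 15 = 135 min. Without the 150-min value it spans 120 min. The plan does not say whether such an AUC is used, extrapolated or dropped. Whether a draw failed is known at the visit, while still blinded; only its handling is open.

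**The case against.** The strongest reply is that PRE-visit sets an earliest date for unblinding and nothing more. A reader might infer that the trial intends to assay and analyse unblinded. No section says so, and the team may well hold the code until the analysis is finished. This reply stands: what the protocol has is an unprotected window.

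A reader might also infer that no sample coding exists. The visible text cannot show that. Consent pages were removed and Figure 1 is not shown, and coding could be described in the missing pages. The point about coding is therefore conditional. The trigger is firmer, because the PRE-visit rule is stated outright and no other section postpones it.

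Third, the blood results leave little room for judgement. The assays are instrument-based, and the analytes, the AUC rule, the test and the threshold are fixed. No section mentions repeat assays or exclusions, so those decisions are possibilities and not plans. This too stands, and it is why the point is minor.

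Finally, the supplier's laboratory would handle stool whatever the unblinding date, and no section says that it knows the treatment order. That question is separate from the trigger. It also does not reach the amino acid comparison, which is the stated aim and the only test specified.

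**Conclusion.** The point holds as a minor, low-cost improvement. The protocol permits unblinding when at least 8 plasma samples and 1 stool sample are not yet assayed. The upper limit of 320 plasma and 40 stool samples requires that no assay has started and that nobody drops out.

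These counts describe how much material is exposed. They do not measure bias. It would be tempting to conclude that the amino acid result is compromised or to attach a percentage to the effect, but the documents do not support either. They give no basis for how many affected decisions would occur or in which direction, and any figure would rest on an invented concentration curve. Any bias is unquantified and probably small.

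The conclusion rests on the PRE-visit sentence being the operative unblinding rule and on no page outside the visible text setting a later one.

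**What to change.** Replace the unblinding sentence in PRE-visit with:

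*Unblinding takes place only after all blood and stool assays are complete, exclusions are recorded, and the analysis dataset is locked.*

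As a second and separate change, unless the pages not shown already cover it, add:

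*Laboratory staff, including those at the supplier's laboratory handling stool, and the analyst work from coded samples and data that do not reveal the condition.*

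The second sentence is the one that addresses the supplier's laboratory; a later trigger alone would not. Its limit should be acknowledged: sequencing may reveal the supplied strains, so masking of stool may be incomplete.

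The cost is two sentences, a code list held for longer and samples labelled by code. No extra visits or samples are needed. If this is already the team's practice, writing it down resolves the point.
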